4.8 Subject Recruitment

Participants will be recruited from the pool of participants at GI Laboratories who have indicated that they are willing to be contacted and asked if they wish to participate in new studies or through online advertisements and posters.

4.9 Selection of participants

The procedure for obtaining informed consent is described in Section 7.1. Volunteers who consent to participate will come to the research centre for a pre-selection visit when subject eligibility will be determined.

4.10 Biochemical Analysis *(note the biochemical analysis method for glucose analysis may change)*

Blood collection tubes will be labeled with the subject's ID, visit date, test meal code, GI Labs protocol number (GIL-1852) and time of collection. After blood collection the tubes containing blood for glucose analysis will be rotated to mix the blood with the anti-coagulant and then placed in a refrigerator until the last blood sample in the set has been collected; after 3 hours the set of 10 tubes will be bundled together with a rubber band and placed in a -20°C freezer until analysis which will be performed within 3 days. Glucose analysis will be performed within 5 days using either the Vitros 350 Chemistry System (Vitros 350 Chemistry System, Ortho Clinical Diagnostics, Raritan, NJ) or a YSI 2300 Stat glucose/lactate analyser (YSI, Inc. Yellow Springs, OH). Analytical coefficient of variation (CV) for

glucose will be calculated by measuring the 0min sample 2 times; typical values range for analytical CV for glucose in our hands is <2%.

The microvette tubes containing blood for insulin will be left at room temperature to allow the blood to clot, centrifuged and the serum transferred to labeled polypropylene tubes and stored at -20°C prior to analysis of insulin. Insulin levels will be measured using the Human Insulin EIA Kit (Alpco Diagnostics, catalog # 80-INSHU-E10.1ii). The typical CV for serum insulin in our hands is about 7%.

5. Data Analysis

5.1 Calculations

The incremental areas under the blood glucose and serum insulin response curves (iAUC), ignoring area below fasting, will be calculated using the trapezoid rule (Wolever et al, 1986, 2004). Fasting glucose and insulin will be taken to be the mean of the concentrations in the 2 fasting samples.

GI symptoms and Satiety calculations – to be added

5.2 Statistical Analysis

No interim analyses are planned. All summaries of demographics, baseline characteristics, efficacy and safety will be performed after all subjects complete both periods and the data collection and query processes are finalized.

Descriptive Statistics: All continuous data will be summarized by number of subjects assessed, mean, standard deviation (SD), median and range (minimum and maximum values). Demographic and baseline characteristics to be summarized include gender; ethnicity; height (m); weight (kg); body mass index (BMI) (kg/m²) and blood pressure (mmHg).

Data will be analyzed using General Linear Model analysis of variance (GLMANOVA). After demonstration of significant heterogeneity, the individual means will be compared using Tukey's test to adjust for multiple comparisons. The criterion for statistical significance will be a 2-tailed $p<0.05$.

6. Study Product

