CRITERIA FOR EVALUATION:	
EFFICACY: Primary outcome is comparison of the glucose IAUC of the Fibersym meal with the control meal.
 
Secondary outcomes: comparison of the insulin (IAUC) of the Fibersym meal with the control meal, comparison of glucose and insulin levels at each time point and satiety scores at each time point.
 
SAFETY: Adverse events.

STATISTICAL METHODS:	Results for all foods in a series will be compared by GLM ANOVA. After demonstrating significant heterogeneity, the significance of the differences will be tested using Tukey method to adjust for multiple comparisons
Ethics Board Approval	The investigator will be responsible for submission of the study to the Western Institutional Research Board. Prior to submission of the application, the sponsors and all co-investigators will be given the opportunity to review the application. Submission of the application will only take place if all parties agree. The Western Institutional Review Board® meets all requirements of the US Food and Drug Administration (FDA), the Department of Health and Human Services (DHHS), the Canadian Health Protection Branch (HPB), Canadian Institutes of Health Research (CIHR) and the European Community Guidelines. Participants will not be enrolled into the study until they have had the study procedures explained to them, had a chance to ask questions, and given their voluntary consent by signing the consent form. Participants who do not understand English will not be enrolled.
Subject Selection Criteria	
Inclusion criteria:
 
 1. Male or non-pregnant females, 18-75 years of age, inclusive 2. Body mass index (BMI) between 18.5 and 35 kg/m² inclusive at screening. 3. Systolic blood pressure < 130mmHg, Diastolic Blood pressure <90mmHg. 4. Willing to maintain habitual diet, physical activity pattern, and body weight throughout the trial. 5. Subject is willing to abstain from strenuous exercise, or consume alcoholic drinks 24hours before study days. 6. Absence of health conditions that would prevent fulfillment of study requirements as judged by the Investigator on the basis

of medical history.

7. Understanding the study procedures and willing to provide informed consent to participate in the study and authorization to release relevant protected health information to the study investigator.
8. Female subjects are willing to use a contraceptive method to avoid pregnancy during the study period.

Exclusion criteria:

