3.4 Withdrawal Criteria

- Withdrawal of consent for any reason
- During the course of the study, the development of an injury or illness or initiation of use of a medication which, in the opinion of [name], makes the subject's continued participation dangerous to the subject or to others, or which may affect the results.
- Failure to follow GI Labs safety guidelines
- Repeated failure to attend at scheduled visits
- Repeated failure to follow the protocol

4. Study Design and Procedures

The study is double-blind with a randomized, cross-over design.

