Visit 2-3: Eligible subjects will be randomized using an online randomization calculator. Eligible subjects will be studied on 2 separate days over a period of 4 weeks or less. Prior to each test meal they will be provided with enough cookies to consume 3 times/day over 3 days and instructed to start consuming these 3 days before their visit. They will also be provided with a calorie appropriate, standard dinner to be consumed on the evening before their test meal. The interval between successive tests will be no less than 6 days and no more than 4 weeks. On each test day, participants will come to GI Labs in the morning after a 10-12h overnight fast (except for water). Participants will be asked to maintain stable dietary and activity habits throughout their participation and refrain from drinking alcohol and from unusual levels of food intake or physical activity for 24h before each test. Before the start of the test meal, subjects will be asked whether they consumed the provided cookies over the last 3 days as instructed and the standard dinner the evening before. Subjects will be asked to complete a 3d record of supplement consumption and whether they consumed the standard evening meal, in addition to a 3d symptom diary before each test visit. If any subject is not feeling well or has not complied with the preceding experimental conditions, the test will not be carried out and will be rescheduled for another day. On each test day, two fasting fingerprick blood samples will be collected at -5min and 0min. Each sample will consist of 2 vials, one for glucose analysis and one for insulin analysis (4—8 drops of blood each). Questionnaires to record satiety and GI symptoms will be administered. Participants will then be given the test food together with 250ml of water and instructed to consume this over 15minutes. Additional blood samples will be collected 15, 30, 45, 60, 90 and 120min after the start of the test meal. Satiety Questionnaires will be administered at the same time intervals. GI symptom questionnaires will be filled out at 2h in addition to fasting.

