4.3 Test Foods

There will be two test foods:

1. Control Cookie
2. Cookie with added Fibersym

The difference in the cookies is the presence of the Fibersym, meals will therefore be matched for available carbohydrate. Both test meals will be consumed with 250ml of water.

During the 3-day pre-feeding period, subject will consume 9 cookies per day with the aim to provide approximately 29g of fibre per day from the Fibersym cookies. For the test breakfasts, the subject will consume approximately 3 cookies containing 50g available carbohydrate. The Fibersym cookies will

deliver approximately 10g of fibre. Once the cookies are baked they will be sent out for macronutrient analysis and the final weight of the cookies fed will be adjusted accordingly.

Table 1: Approximate composition of the test meals*

	Approx. # cookies	Weight (g)	Protein (g)	Fat (g)	Total carbohydrate (g)	Dietary Fibre (g)	Available carbohydrate (g)
Control Cookie	3	90	3.4	10.5	50.2	0.2	50
Fibersym cookie	3	100	3.4	10.5	60.2	10.2	50

* Once the cookies are baked they will be sent out for macronutrient analysis and the final weight of the cookies fed will be adjusted accordingly.

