4.6 Satiety

Subjective measurements of palatability, motivation to eat and physical comfort will be assessed using visual analog scales (VAS) (Appendix 3) at the same time points blood samples are collected. Each of the questions on the VAS is a 100 mm line anchored at each end with opposing statements (Rogers and Blundell 1979). For instance, fullness is assessed with the following statement on the left side of the line “not full at all” with the following statement to the right side of the line “As full as I

have ever felt". Participants make a vertical mark on the line at a point that they feel reflects their feelings at the moment the test was taken. Scores will be assessed by measuring the distance between the intersection of the mark on the line and the left end of the line (see Appendix 3).

The Motivation to Eat questionnaire includes 4 questions:

Q1: How strong is your desire to eat? ("very weak" to "very strong")

Q2: How hungry do you feel? ("not hungry at all" to "as hungry as I have ever felt")

Q3: How full do you feel? ("not full at all" to "as full as I have ever felt")

Q4: How much do you think you could eat now? ("nothing at all" to "a large amount")

Average appetite score is calculated as a summary measure using the following equation:

$$\text{Average appetite} = [Q1 + Q2 + Q4 + (100 - Q3)] / 4$$

Since Question 3 assesses fullness, it has opposite anchors at each end of the 100 mm line compared to the other 3 questions. Therefore, Q3 is subtracted from 100 in the equation to adjust for this difference.

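### If the ANOVA and Tukey step compares the two foods, as the synopsis says, it adjusts nothing, and the secondary tests at six post-meal times lack familywise control

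*Combined protocol and SAP*

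**What the plan says.** Section 5.2 gives the operative rule: "Data will be analyzed using General Linear Model analysis of variance (GLMANOVA). After demonstration of significant heterogeneity, the individual means will be compared using" (the method named is Tukey's test), at a two-sided 5% criterion. It lists no model terms and names no family of tests.

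The synopsis (Statistical Methods) says what enters the ANOVA: "Results for all foods in a series will be compared by GLM ANOVA". It adds that, after heterogeneity is shown, "the significance of the differences will be tested using Tukey method to adjust for multiple comparisons". Section 4.3 fixes the number of foods: "There will be two test foods". Section 4 gives the design: "The study is double-blind with a randomized, cross-over design".

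The synopsis lists among the secondary outcomes "comparison of glucose and insulin levels at each time point and satiety scores at each time point", and section 2.2 repeats the time-point aim for glucose and insulin. Section 4.1 sets the times: "Additional blood samples will be collected 15, 30, 45, 60, 90 and 120min after the start of the test meal".

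No other multiplicity rule appears, and the time-point comparisons are not labelled exploratory. For satiety, section 4.6 says "Average appetite score is calculated as a summary measure using the following equation", but section 5.1 records that the GI symptom and satiety calculations have still to be added.

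**The concern.** Tukey's method protects a set of pairwise comparisons among several means. With two foods there is one pair and nothing to protect. The multiplicity in this trial comes from repeating the food comparison at six times for each outcome, and a Tukey step across foods does not reach that.

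What is at stake is how the secondary time-point results will be read. A p-value reported as Tukey-adjusted at, say, 30 minutes would look corrected for the number of looks when it was not. One significant time out of six could then be presented as a confirmed effect on the glucose or insulin profile.

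**Working it through.** **Inputs.** Two foods (section 4.3); 15 subjects, each taking both foods (sections 3.1 and 4); six post-meal times (section 4.1); two-sided 5% (section 5.2). The documents give no between-time correlations, so those below are assumptions. The 5% criterion is the only numerical figure in the plan that bears on this point.

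**1. Tukey and the ANOVA gate with two means.** With subject and food in the model, error df = 15 − 1 = 14.
- Tukey: q(0.95; 2, 14)/√2 = 3.0332/1.4142 = 2.145.
- Unadjusted t: t(0.975; 14) = 2.145.
- ANOVA gate: F(0.95; 1, 14) = 4.600 = 2.145².

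All three are one test. At t = 2.5 each gives p = 0.0255. At 13 df, as with one further model term, all three critical values are 2.160, so the identity does not depend on the df.

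**2. Error across six times on that reading, no true effect at any time.**
- Independent times: 1 − 0.95⁶ = 0.265.
- Simulated paired t-tests, n = 15, AR(1) by sample order with adjacent correlation 0 / 0.5 / 0.8 / 0.9: 0.265 / 0.239 / 0.179 / 0.139.
- Equal correlation between all times instead, at 0.5 / 0.8 / 0.9: 0.211 / 0.145 / 0.114.

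The range for one outcome is thus about 11% to 26%. Glucose and insulin together make 12 tests; if all were independent the figure would be 1 − 0.95¹² = 0.460, an upper illustration.

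**3. Reading with Tukey over food-by-time means.** There are 2 × 6 = 12 means and 15 × 12 = 180 observations, so error df = 180 − 1 − 14 − 11 = 154.
- Tukey: q(0.95; 12, 154)/√2 = 3.32, against 1.98 unadjusted.
- Chance of a false positive among the six food contrasts: 0.7% if independent and 2.8% at AR(1) 0.8, assuming equal variance at all times.

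This adjusts, and more than needed: it covers 12 × 11/2 = 66 pairs when six are of interest.

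**4. Reading with one omnibus gate per outcome, then unadjusted time-point tests.** With a multivariate test of no food difference at any time as the gate, n = 15:
- No true effect anywhere: about 4% (independent) to 2–3% (AR(1) 0.8).
- One time truly different: the gate tends to open, and the chance of a false positive among the other five times is about 13% to 22%, depending on the correlation and the size of the true effect.

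**5. Holm across the six times within an outcome.**
- Error with no true effect: 4.9% if independent, 3.7% at AR(1) 0.8.
- Across three outcomes, taken as independent: 1 − (1 − 0.049)³ = 14% and 1 − (1 − 0.037)³ = 11%.
- Power at one time for an assumed true effect of 1.0 SD of the paired differences at that time only: about 95% unadjusted, about 77% with Holm.

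**The case against.** The strongest reply is that section 5.2, the operative text, does not mention foods. It speaks of data and of individual means, and the plan elsewhere calls for comparisons at each time point, so a model containing time is plausible. On one such reading Tukey over-corrects (step 3). On another, a single gate per outcome holds the error when nothing differs (step 4), and the 26% and 18% do not apply. This stands, and it limits the finding to the reading that the synopsis supports. It does not remove the need for a change: the same time-point result could be judged against 2.145 or 3.32, and the text does not say which.

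A second reply is that these are secondary profiles in a 15-subject food study and that familywise control for them is partly convention. That is fair, and it is why a descriptive label is an acceptable remedy. But the plan itself promises an adjustment, so it should either deliver one or withdraw the promise.

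A reader might infer that the trial has no error control at all, or that the primary conclusion is inflated. The documents support neither. Every test keeps its own 5% level, and the primary glucose IAUC is a single comparison, as is the insulin IAUC. Nor can six tests be asserted for satiety: the scores are taken whenever blood is drawn, which includes fasting, and the calculations are openly unfinished.

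**Conclusion.** The concern holds in a limited form. If foods are what the ANOVA and Tukey step compares, the identity with the unadjusted test is exact and needs no assumption about the data. The planned glucose and insulin comparisons at six times then have no familywise control, with a chance of at least one false positive per outcome of about 26% under independence and 18% at an assumed AR(1) of 0.8, when no time truly differs.

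A reader might go further and conclude that the Tukey step is useless however the model is built. That does not follow: over 12 food-by-time means it would adjust, and an omnibus gate would protect when no time differs, though not once some times do. What is certain on every reading is that the model and the family of tests are not named. Confidence is moderate, because the diagnosis turns on the reading. The matter is confined to secondary outcomes, but it should be settled before data are seen.

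**What to change.** First, state in section 5.2 and the synopsis whether time is a factor in the model. Then:

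- **Foods compared separately at each time.** Replace the Tukey step with one of two rules. (a) Holm across the six post-meal times within each outcome, with a statement that error is controlled per outcome and not across outcomes. (b) Label the time-point results descriptive, with unadjusted 95% CIs and no significance claims.
- **Food-by-time model.** Name its terms and limit the adjusted contrasts to the six food differences, rather than all 66 pairs.

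Apply the same rule to satiety once section 5.1 is completed, fixing there which score and which times are tested. The average appetite score in section 4.6 is one option.

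The cost is wording. Option (a) also lowers power at a single time from about 95% to 77% for the assumed 1.0 SD effect; option (b) avoids that loss but gives up significance claims at individual times. The primary glucose IAUC and the insulin IAUC tests need no change on this account.

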6.1 Blinding, Packaging and Labelling

The product label will display the subject number, subject initials, product ID, ingredients statement, GIL repacked date, expiration date, researcher name and telephone number, investigational use statement, and allergy warnings (if needed). Study Product Intake Logs will be completed upon dispensation of study product to each subject.

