Appendix 3: Satiety Questionnaire.....	24

Study Synopsis

STUDY TITLE:	Comparison of postprandial glycemic and insulinemic response to a Cookie with or without added Fibersym after three days of pre-feeding: An acute, double-blind, randomized controlled clinical trial
STUDY NUMBER/ VERSION DATE:	GIL-1852; version: June 31, 2018
INVESTIGATORS:	GI Labs: [name], PhD; [name]
SPONSOR:	MGP Ingredients, Inc, Contact: [name], VP Ingredients R&D and Chief Science Officer
STUDY SITE:	Glycemic Index Laboratories, Inc. (GI Labs)
STUDY OBJECTIVE(S):	Primary Objective: to compare the postprandial glucose incremental area under the curve (IAUC) after the Fibersym containing carbohydrate load with the glucose IAUC after the control meal
INTERVENTION PRODUCT	Fibersym® is a resistant modified wheat starch in which over 85% of the total starch is resistant starch as measured by AOAC method 991.43. Fibersym can easily be added to food formulations as it provides a smooth texture, neutral flavour and white color.
STUDY POPULATION	Healthy adult males or females (n=15), aged 18-75 years with BMI between 18.5 and 35 kg/m ² . Each subject will have to fulfill all inclusion criteria and will not be allowed to meet any of the exclusion criteria.
TEST MEALS:	
 1. Control Cookie 2. Cookie with added Fibersym 
The difference in the cookies is the presence of the Fibersym, meals will therefore be matched for available carbohydrate.

STUDY DESIGN AND RATIONALE	
Design: acute, double blind, randomized, controlled clinical trial. Subjects will come in fasting and be given either the Control or Fibersym containing cookie. Postprandial glucose and insulin levels will be measured over 2 hours.
 
As Fibersym is recommended to be consumed on a daily basis, for 3 days prior to each test meal visit, subjects will be given cookies to be consumed 3 times daily for 3 days, ie control cookies will be consumed for 3 days before the control cookie test meal and Fibersym cookies

	
before the Fibersym cookie test meal. Each subject will be provided with enough cookies to consume 1 cookie with each meal (breakfast, lunch and dinner) over the 3 days. The Fibersym containing cookie will deliver about 29g/day of dietary fibre.

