Appendix 1—Fibersym Nutritional Data

TECHNICAL DATA

 [name] • [contact] • www.mgpingredients.com

Fibersym® RW

U.S. Patent No. 5855946

Product Description

Fibersym® RW is a resistant wheat starch that typically delivers greater than 85% (d.b.) Total Dietary Fiber (AOAC Method 991.43). Fibersym® RW has a low water-holding capacity that allows for enhanced crispness and ease in formulating higher levels of inclusion to achieve labeling benefits. Providing a smooth texture, neutral flavor and white color, Fibersym® RW is a nearly invisible source of fiber. Applications include bakery products, pasta and nutritional food products to boost fiber content, snack foods and batter products to enhance crispness, breakfast cereals to increase bowl life and maintain crispness, and nutritional products targeting controlled glucose release.

Property	Typical Value	Test Method
Total Dietary Fiber	85% min. (dry basis)	AOAC 991.43
Appearance	Fine powder	Visual
Color	White to off-white	Visual
Odor	Bland	Sensory
Moisture*	< 12%	AACC 44-15
pH	4.5 – 6.5	25% Solids
Ash	3.0% maximum	AACC 08-03
Protein, % (N x 5.7 As is)	0.5% maximum	AACC 46-30 Combustion

*The moisture content can vary depending on environmental conditions during storage.

Microbiological

Aerobic Plate Count	10,000 cfu/g maximum	AOAC 990.12
Mold and Yeast	200 cfu/g maximum	AOAC 997.02
Escherichia coli	< 10 / g	AOAC 991.14
Salmonella spp.	Negative in 375 grams	AOAC 2003.09

Packaging, Storage, and Shelf Life

Fibersym® RW is packaged in multi-ply Kraft bags with a net weight of 50 lbs. (22.7 kg) or 25 kg (55.1 lbs). Various tote sizes and bulk also available. Typical bulk density (packed) is 48 lbs./cubic ft. (769 g/L). The product should be stored in a cool, dry, and sanitary area to achieve maximum stability. Shelf life is two (2) years from the date of manufacture when stored under these conditions.

Ingredient Labeling Statement

Modified Wheat Starch. (Fibersym® RW is Phosphated distarch phosphate wheat starch with CAS Number 977043-58-5 and INS Number 1413.)

Disclaimer Statement

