Total dietary fiber meets the above specification at point of manufacture. Additional processing may affect the fiber content of products containing any resistant starch. Due to the nature of the testing procedure, TDF results may vary between laboratories, and it is crucial to use the temperature of 100°C as specified in the AOAC 991.43 test for best reproducibility. Final fiber content may differ from software-based calculations and it is better determined by testing.

The information and recommendations in this document are based on experience and analysis using standard procedures, and are believed to be accurate and reliable. However, they serve merely as typical guides, and are presented in good faith for the benefit of customers. No guarantee, expressed or implied, is made regarding accuracy of the analysis, patent infringement, liabilities, or risks involved from the application of this product.

Issued: 1/23/16
 Revision: 14
 Approved: [name]
 Page 1 of 1

TECHNICAL DATA

 [name] • [contact] • www.mgpingredients.com
FIBERSYM® RW
TYPICAL NUTRITIONAL DATA
Nutrient Information (per 100 grams)

Water	10.5
Calories, insoluble fiber subtracted*	39
Protein (grams) (Nx5.7)	0.15
Total Fat by GC (grams)	0.5
Saturated Fat (grams)	0.2
Monounsaturated Fat (grams)	0.04
cis-cis Polyunsaturated Fat (grams)	0.23
trans Fat (grams)	0.00
Carbohydrates (grams) (by calculation)	87.6
Total Dietary Fiber (grams) (as-is) †	80
Soluble Fiber (1g)	
Insoluble Fiber (79g)	
Ash (grams)	1.25
Calcium (milligrams)	21.8
Iron (milligrams)	<1.0
Sodium (milligrams)	308
Cholesterol (milligrams)	<1.0
Potassium (milligrams)	<3.0

Sugars by HPLC (per 100 grams)

Total Sugar	0.0
Fructose	<0.1
Glucose	<0.1
Sucrose	<0.1
Maltose	<0.1
Lactose	<0.1

Vitamins

Vitamin D, Total	<1 ug/100g
Vitamin A, Retinol	<100 IU/100g
Vitamin C	1.19 mg/100g

This product is not produced with added sugars.

* Per 21 CFR 101.9(c)(1)(i)(c)

† Note: Total Dietary Fiber on a dry basis (db) is typically > 90%, with a minimum db specification of 85%.

The information and recommendations in this document are based on experience and analysis using standard procedures, and are believed to be accurate and reliable. However, they serve merely as typical guides, and are presented in good faith for the benefit of customers. No guarantee, expressed or implied, is made regarding accuracy of the analysis, patent infringement, liabilities, or risks involved from the application of this product.

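### Section 6.1 calls for an ingredients statement on each subject's product label but gives no blinding procedure and no rule that both cookies carry common text; 7.4 also passes the allocation to the Principal Investigator without a stated need

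*Combined protocol and SAP*

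**What the plan says.** The opening of Section 4 states: "The study is double-blind with a randomized, cross-over design". The synopsis also calls the trial double-blind.

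Section 6.1 (Blinding, Packaging and Labelling) is the only section whose heading mentions blinding. Its content is a list of label items and a sentence on intake logs. On the label it says: "The product label will display the subject number, subject initials, product ID, ingredients statement, GIL repacked date". The list goes on to expiry date, contact details, an investigational-use statement and allergy warnings if needed.

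Section 4.3 says that the two cookies differ by the presence of Fibersym. The ingredient labelling entry in Appendix 1 gives its name as "Modified Wheat Starch".

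Subjects handle the product themselves. The synopsis says that "control cookies will be consumed for 3 days before the control cookie test meal", with the corresponding arrangement for the Fibersym cookie, and Section 4.1 has the cookies supplied before each test visit.

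The outcomes open to expectation are rated by the subject. On satiety, 4.6 says: "Participants make a vertical mark on the line at a point that they feel reflects their feelings". Section 4.5 uses a 100 mm scale for the severity of GI symptoms.

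Section 7.4 has the Principal Investigator told, within 48 hours, both what the reportable adverse event was and which treatment the participant was allocated. No condition is attached to the second item.

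**The concern.** A double-blind claim needs a mechanism, and the section where a reader would look for one does not supply it. It supplies a list of label items, one of which could tell the two products apart. If each pack carries an accurate list for its own formulation, the Fibersym pack would be expected to name a modified starch that the control pack does not.

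At stake are the comparisons of satiety scores and GI symptoms, both secondary objectives in 2.2, where GI symptoms are also listed under safety. A subject who believes that a given cookie is the fibre product may report more fullness or more bloating for that reason alone. In a crossover, each subject's two ratings are compared with each other, so such a belief would act directly on the within-subject difference.

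The notice in 7.4 is a separate matter, with a different person unblinded and a different route. It is a stated rule, so it needs no inference about labels.

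**Working it through.** The plan gives no figure to reproduce on this point. The check sets the provisions side by side.

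**Label route**

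1. *Is a blinding procedure given anywhere?* Section 4 and the synopsis declare it. Section 4.7 covers only how treatment orders are generated and assigned. Section 6.1 lists label items. Sections 6.2 and 7.6 say who may be given product. None of these says who is blinded, who holds the code, or how the two products are made to look alike on the pack.
2. *Is there any coding?* Section 6.1 lists a product ID, and 4.10 puts these items on blood tubes: "visit date, test meal code, GI Labs protocol number". Both suggest some coding. Neither is said to be neutral, and a code does not mask a differing ingredient list printed beside it.
3. *Would accurate product-specific lists differ?* Table 1 gives 10.2 g fibre for the Fibersym meal and 0.2 g for control, so 10.2 − 0.2 = 10.0 g comes with the added ingredient. It is a deliberate main addition, so an accurate list for that cookie would be expected to name it and the control list to omit it.
4. *Who would see the labels?* Two products, two periods, and take-home supply before each test visit: every subject who completes both periods receives both, up to 15 of 15.
5. *Which outcomes are exposed?* Satiety (4.6) and GI symptoms (4.5) are marked by the subject. Glucose and insulin are laboratory measurements (4.10) with IAUC computed by the trapezoid rule (5.1).

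**Adverse event route**

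1. *Which events?* Under 7.4, reportable events are those that are unexpected, at least possibly related to taking part, and suggestive of greater risk than previously recognised.
2. *What is disclosed?* The participant's allocation, for every such event, whether or not knowing it is needed.
3. *What follows in this design?* With two products and two periods, naming the product in one period fixes the other by elimination. One notice therefore unblinds the investigator for both of that participant's periods.

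**The case against.** The strongest reply is that 6.1 never says that the ingredients statement is product-specific. One common statement on both packs would satisfy it fully, and the product ID and test meal code fit a coded supply. That stands. A reader might infer that 6.1 contradicts the double-blind declaration, or that subjects will in fact be unblinded. The documents support neither. The recipes and label texts are not given, so that the labels differ is an expectation about what accurate product-specific text would say.

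It is also fair that harm needs several further steps. The subject must read the list, notice a generic name that mentions neither Fibersym nor fibre, connect it with the test product, and then rate differently. A reader might picture the two packs compared side by side. The schedule does not describe that: cookies are supplied before each test and tests are at least 6 days apart, so direct comparison would need a kept pack. Reading each list in turn remains possible.

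A reader might also extend the concern to the primary result. The documents give little ground for that, because the primary outcome is a laboratory measurement.

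On 7.4, the reportable events are narrowly defined, 7.5 says that no adverse events related to this starch have been reported, and the trial has 15 subjects, so few or no notices are likely. The notice goes to the investigator and not to the subject, so it does not add to the label route. Both limits are accepted.

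What remains is that the declared blinding has no stated procedure, that the ordinary way of following 6.1 could put a distinguishing list in subjects' hands, and that 7.4 discloses allocation with no test of need.

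**Conclusion.** The point holds as a minor one. Section 6.1 leaves the blinding of the product unspecified and requires a label item that would be expected to distinguish the cookies if it were written for each product. The consequence is confined mainly to the self-rated satiety and GI symptom comparisons. Its size cannot be computed, because the documents give neither the label texts nor any basis for estimating how expectation would shift the ratings. The share of Fibersym in the cookie would not measure it either.

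The label conclusion rests on two assumptions: that the statement is specific to each product, and that it reaches the subject in legible form. If the sponsor already intends common text, one sentence in 6.1 settles the matter. The adverse event conclusion rests only on the wording of 7.4 and on the Principal Investigator being among those meant to be blinded, which the plan does not say.

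**What to change.** **Section 6.1.** Require one combined ingredient and allergen statement, covering both formulations, on both products. Use a neutral product ID coded by subject and period, so that decoding one subject does not decode the others. Let only subject identifiers, code and dates vary between labels. State who is blinded and which role holds the code.

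**Section 7.4.** Send the adverse event notice with the code only. Break the code through a separate, documented step when knowledge of the allocation is needed.

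**Cost.** Label text and a few sentences. Subjects would see a combined list and not a product-specific one. Since each subject is due to eat both cookies, and 3.3 excludes known intolerance to any ingredient of the study products, the combined list still covers what each subject will consume. It does not remove cues from the cookies themselves: Table 1 gives test portions of about 90 g and 100 g, and appearance may differ.
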